Sequence and Timing of visits: Each subject will undergo up 2 visits to the lab. One sleep study will be conducted while wearing CPAP for the entire night. The second sleep study will be conducted using nasal dilator strips (NDS) as a placebo, instead of wearing CPAP, the entire night. NDS have been used in other studies as a CPAP placebo and have no impact on OSA severity [6]. The studies will be performed in random order, occurring >1 week apart and no longer than 3 months apart. To maximize chances of eliciting OSA during the non-CPAP study night, patients will be asked to refrain from CPAP use, for two nights preceding their non-CPAP study night. They will be provided with ClearPassage® NDS to use at home during CPAP withdrawal nights. This will ensure CPAP “washout” since therapeutic carryover effects of CPAP have been observed in some studies[7]. Patients who were previously enrolled in the single-night study (within-night CPAP withdrawal) will be invited to return for these additional sleep studies.

Study eligibility: To be enrolled in the study, participants will need to undergo a screening questionnaire and meet inclusion/exclusion criteria. They will need to provide written consent for participation. To avoid issues of CPAP intolerance, participants must also be accustomed to using CPAP, and report that they are capable of sleeping with CPAP on.

As of March 16, 2020 (or approval of this eFormA update), and in order to mitigate risks related to COVID-19 exposure to participants and study team, phone screening procedures will be completed from the study team members' home using a connecting service, such as Google Voice or Skype Voice-to-IP to protect study team members' personal contact information while allowing them to continue job functions from a safe location. Participants will be notified of the change in procedure.

Consent: In order to minimize the need for research-only in-person visits, telemedicine visits may be substituted for in person clinical trial visits or portions of clinical trial visits where determined to be appropriate and where determined by the investigator not to increase the participants' risks. Prior to initiating telemedicine for study visits

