The primary outcomes is nocturnal plasma FFA levels. The main independent variable is OSA versus CPAP exposure during sleep. Since FFA are measured multiple times per subject per night, we will perform mixed linear model analysis using condition as a fixed factor and subject ID as a random factor. Sleep physiology that is measured on a continuous basis will be condensed into 30 minute bins to create a parallel data structure with metabolic parameters. As a secondary analysis, we will also examine whether there are patient-specific (“static”) determinants of FFA level during sleep such as age, sex, or body mass index and whether these variables interact with sleep (“dynamic”) variables such as OSA severity. We hypothesize that OSA exposure increases FFA, compared to CPAP. We will then examine whether sleep physiology (e.g. AHI, arousals, heart rate) is dynamically associated with FFA, and whether urine catecholamine levels are associated with increases in FFA. For variables measured once (RHI, morning lipid profile) or averaged (e.g. nocturnal FFA level) we will perform one-way ANOVA for comparisons. We will also compare sleep physiology between the 3 nights, examining variables such as apnea hypopnea index, metrics of hypoxia, and sleep architecture/duration. Data analysis will be performed with a biostatistician and described under the “Study Statistics” section.

b. Study duration and number of study visits required of research participants.

Each study subject will make two overnight visits to the sleep lab. Subjects will be screened with an initial telephone interview. During this screening, only information necessary to assess eligibility for the study will be collected, or information voluntarily provided by the patient to initiate or maintain correspondence. Subjects without any of the self-reported exclusionary criteria will be scheduled for a face-to-face visit for further screening. At this visit, eligibility for

participation in the study protocols will be confirmed. Urine screening for pregnancy in women of child-bearing age will also be performed.

c. Blinding, including justification for blinding or not blinding the trial, if applicable.

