- *Sex-specific effects:* This will be assessed by (1) comparing mean change in FFA level during CPAP withdrawal between men and women (unpaired T-test); (2) modeling mean FFA level as a function of sex (as well as sex x BMI interactions) in multivariable regression. We hypothesize that men will exhibit greater OSA-induced FFA elevation than women, with or without adjustment for OSA severity and fat distribution.
- *Effects of OSA severity or sympathetic activation:* We will apply linear mixed models with FFA as the outcome, OSA severity or SNS variables (e.g. AHI, ODI, arousal index, HR, urine catecholamines) as fixed factors and subject ID as the random effects variable. Iterative time lags will be used to account for potential delayed effects of dynamic variables. We hypothesize that plasma FFA level will be independently associated with AHI, arousals from sleep, HR elevation, or urine catecholamine level.
- *Identification of robust “responders”:* We will examine FFA elevation as a dichotomous outcome, defining “FFA responders” as those who exhibit Δ FFA $\geq 10\%$ during CPAP withdrawal (subject to change depending on the distribution of responses; the 10% threshold is based on a median increase in nocturnal FFA of $\sim 8.9\%$ in our preliminary data). OSA severity, sleep architecture, sex, age, and fat mass will be compared between responders and non-responders.
- *Identification of potential “downstream” effects of FFA elevation.* We will test the association between nocturnal FFA profile and other cardiometabolic outcomes (e.g. morning OGTT, endothelial function). Multivariable regression will be used to adjust for potential confounders such as age, sex, and BMI.
- *Identification of potential circulating genetic/epigenetic changes.* An exploratory aim of this study is to examine effects of CPAP withdrawal on peripheral blood mononuclear cell (PBMC) gene expression. We will utilize real-time polymerase chain reaction (RT-PCR) arrays (Qiagen MAP Kinase RT2 Profiler and Human Toll-Like Receptor (TLR) Signaling Pathway RT2 Profiler PCR Arrays, Qiagen, Valencia, CA) to characterize gene changes that result from nocturnal hypoxemia.

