Sample Size: One of the stated goals of this study is to examine sex-specific lipolytic responses to CPAP withdrawal. We base our sample size on the ability to detect a difference in FFA elevation between men and women. In the 20 non-diabetics of our preliminary data, the average Δ FFA during CPAP withdrawal was 0.047 ± 0.04 mmol/l in men (n=13), and 0.021 ± 0.04 mmol/l in women (n=7). This yields a medium effect size (Cohen's $d = 0.65$). To detect a sex difference at 80% power at a significance level of 0.05, requires a sample size of 78 (39 men and 39 women). We anticipate potential technical problems (e.g. IV failures, hemolysis, and poor sleep efficiency) leading to loss of 15% data. Therefore, our target enrollment will be 92 subjects.

Early stopping rule

At any point in the study, the subject may decline to participate. Indications for stopping are the development of severe adverse events. The DSMB and IRB will be informed of any adverse events. Any serious adverse events will result in study discontinuation.

7. Risks

- a. Medical risks, listing all procedures, their major and minor risks and expected frequency.

Venipuncture: May be associated with discomfort and bruising. Infection or irritation (phlebitis) can occur at the IV site.

Phlebotomy: In total, the blood collected will be approximately 174 cc (as compared to approximately 350 mL during a donation). Theoretically, if too much blood is lost, this could lead to low blood pressure and cardiovascular stress or dizziness.

Withdrawal of CPAP: During abstinence from CPAP over 3 days, subjects may experience relatively unrefreshing sleep. During the night, they may experience arousals from sleep, morning headache. During the daytime, they may experience subjective and/or objective daytime sleepiness. The risk of sleepiness contributing to an accident such as work-related injury or motor vehicle collision is also increased. Chronically, OSA is associated with increased risks of hypertension, diabetes, stroke, and ischemic heart disease. In a recent study on the effects of 2-weeks of CPAP withdrawal, there were modest and gradual increases in daytime blood pressure, heart rate, and triglycerides⁷. Risks of stopping CPAP for 2 weeks is therefore a low-risk, high yield research method. In this study, withholding CPAP for a few days is associated with even fewer risks.

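### Night order is randomised but no visit or order term enters the primary FFA model or the t-test that sizes the trial; adding one costs a degree of freedom and can only modestly lose, and may gain, precision

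*Combined protocol and SAP*

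**What the plan says.** Section 4a (Sequence and Timing of visits) describes a two-period crossover, one night on CPAP and one on nasal dilator strips: "The studies will be performed in random order, occurring >1 week apart and no longer than 3 months apart".

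For the primary outcome, Data Analysis and Anticipated Outcomes states: "we will perform mixed linear model analysis using condition as a fixed factor and subject ID as a random factor". Study Statistics, Specific Aim 1, adds only that CPAP/OSA exposure is the independent variable.

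For sex, Study Statistics, Specific Aim 2, gives two analyses: "comparing mean change in FFA level during CPAP withdrawal between men and women (unpaired T-test"), and "modeling mean FFA level as a function of sex (as well as sex x BMI interactions) in multivariable regression".

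The Sample Size paragraph rests on the first of these: "We base our sample size on the ability to detect a difference in FFA elevation between men and women". Its inputs are changes of "0.047 ± 0.04 mmol/l in men (n=13), and 0.021 ± 0.04 mmol/l in women (n=7"), and its result is "To detect a sex difference at 80% power at a significance level of 0.05, requires a sample size of 78 (39 men and 39 women").

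No visit, period, order or sequence term appears in any described analysis. Elapsed time is mentioned under Specific Aim 2, but as a sleep-specific factor within the night. The two nights without CPAP before the strip night deal with carry-over of treatment, which is a different matter. The method of allocating order is not described, and nothing is said about blocking or stratifying it by sex.

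**The concern.** In a two-period crossover, any systematic difference between first and second visits is mixed into each subject's treatment difference, with a sign that depends on order. When the target is the mean difference over all subjects and the orders are balanced, this cancels. The comparison that sizes this trial is different: it sets the changes of men against the changes of women. There the visit difference does not cancel subject by subject. It becomes extra scatter in the outcome of the t-test.

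A first-visit effect is possible in this design: an overnight stay in a research unit with two IV lines and repeated sampling, with up to three months between nights. What is at stake is the precision of the sex comparison and, to a lesser degree, of the primary CPAP contrast. The design already randomises the factor that would remove this scatter, so leaving it out gives up precision that is nearly free.

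**Working it through.** **Inputs.** From the Sample Size paragraph: sex difference 0.047 - 0.021 = 0.026 mmol/l; SD of change 0.04 in each sex; 39 per sex; alpha 0.05; 80% power; 15% data loss. Assumed: the visit shift p (a quantity in mmol/l, not a p-value), shown over a range; change taken as strip night minus CPAP night, which the documents imply but do not define; a two-sided test, since sidedness is not stated.

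**The plan's own figure.** d = 0.026 / 0.04 = 0.65, as stated. A two-sided t-test needs 38.14 per sex, rounded up to 39, so 78 in all, with power 80.9%. A one-sided test would need only about 30 per sex, so two-sided is what was used. Enrolment: 78 / 0.85 = 91.8, rounded up to 92. The stated sizes reproduce from their inputs.

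**Effect of a visit shift.** Let s = +1 or -1 code the order. Then

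change = sex mean + s·p + error.

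With orders in equal proportion, s·p has mean 0 and variance p².

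*Case A: 0.04 excludes the visit shift.* The unadjusted SD is √(0.04² + p²). With an order term it returns to 0.04.

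*Case B: 0.04 already includes it.* The unadjusted SD is 0.04, as planned. With an order term it falls to √(0.04² - p²).

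Two-sided power at 39 per sex:

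| p (mmol/l) | A: unadjusted SD | A: d | A: unadjusted power | B: adjusted SD | B: adjusted power |
|---|---|---|---|---|---|
| 0 | 0.0400 | 0.650 | 80.9% | 0.0400 | 80.9% |
| 0.005 | 0.0403 | 0.645 | 80.3% | 0.0397 | 81.5% |
| 0.01 | 0.0412 | 0.631 | 78.5% | 0.0387 | 83.3% |
| 0.02 | 0.0447 | 0.581 | 71.7% | 0.0346 | 90.5% |

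In Case A the order-adjusted regression keeps power at about 80% whatever p is (simulated, 6,000 runs per setting, p from 0 to 0.04: 80.0% to 80.6%). In Case B the unadjusted test has its planned 80.9% throughout.

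**Imbalance of order between the sexes.** If one order is more common among men than among women, the estimated sex difference shifts by 2p × (share among men - share among women). For example, with 23 of 39 men and 16 of 39 women in one order and p = 0.02, the shift is 2 × 0.02 × 7/39 = 0.0072, or 28% of 0.026. Under simple 1:1 randomisation a gap of 7 or more between the two counts occurs in about 14% of trials.

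**This is the same variance as above.** Over simple randomisation the shift has mean 0 and SD 2p·√(0.25 × 2/39) = p·√(2/39). The squared standard error of the unadjusted sex difference in Case A is

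(2/39)(0.04² + p²) = (2/39)·0.04² + (2/39)·p²,

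and the second term is exactly the variance of that shift. At p = 0.02 the two parts are 0.0091² and 0.0045², giving a standard error of 0.0101. Simulated type I error of the unadjusted test, averaged over randomisation, is 4.8% to 5.4%.

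**The case against.** The strongest reply is that the harm depends on a number the documents do not contain. At p = 0.01 the loss is about 2 points of power, and at 0.005 under 1 point. A shift of 0.02 would be about as large as the whole mean change seen in women (0.021). That stands: the omission is certain, its cost is not.

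Several stronger readings are tempting, and the documents do not support them.

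- *That the trial is underpowered.* The paragraph does not say which design produced the SD of 0.04; section 4a mentions an earlier single-night study. If 0.04 came from randomised two-night data with a similar visit shift, there is no shortfall against 80%.
- *That the sex estimate is biased, in addition to losing power.* It is unbiased over the randomisation. A shift exists only conditionally on an imbalance that has occurred, and it is already counted in the inflated SD.
- *That order is unbalanced within sex.* The text says only that order is random. All one can say is that no blocking or stratification is described.
- *That the protocol itself predicts a first-night effect.* The remark in section 4d linking stress and sleep loss to lipolysis is about patients new to CPAP, and it justifies enrolling established users.

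There are also mitigating features: subjects accustomed to CPAP, sampling from an adjacent room, optional repeat nights after poor sleep, and returning participants who may know the procedures. These may shrink a visit effect but do not rule one out. For the primary CPAP contrast, random order gives protection in expectation, so the gain there is in precision only.

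None of this argues against adjustment. If p is zero, the term costs one degree of freedom.

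**Conclusion.** The point holds as a matter of efficiency and good crossover practice. The plan randomises night order and then leaves it out of both the primary FFA model and the test that sizes the study. The arithmetic behind 78 and 92 is correct, and the gap is in the analysis model.

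The size is conditional on p and on where the SD of 0.04 came from. For p between 0.005 and 0.02 mmol/l, either the unadjusted sex test runs at about 80% down to 72% power where adjustment would hold about 80%, or it runs at its planned level where adjustment would reach about 82% up to 91%. Below about 0.01 mmol/l the difference is under 3 points either way. The figures also assume equal proportions in each order, the same shift in both sexes, and 39 evaluable subjects per sex. The omission is clear from the text; the practical loss may be negligible.

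**What to change.** 1. Add visit number (first or second) as a fixed effect in the primary FFA mixed model.
2. Replace the unpaired t-test by a linear regression of each subject's FFA change on sex and order. Use one order variable, defined once and consistent with the visit number in the mixed model.
3. Define that variable in advance for the two ambiguous cases: nights repeated for technical failure or poor sleep (Repeat sleep testing), and participants returning from the single-night study (section 4a).
4. For subjects not yet randomised, block order within sex. For those already randomised, items 1 to 3 suffice, provided the order of nights is on record.
5. State in the Sample Size paragraph which design the SD of 0.04 came from.

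The cost is one degree of freedom per model, some wording in Study Statistics and, if recruitment continues, a stratified order list. There is no added burden on participants, and neither 78 nor 92 needs to change: with the order term, power stays at about 80% if 0.04 is free of visit variance and rises if it is not.

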Following centrifugation, plasma will be transferred to cryovials for storage. The final morning sample at time of awakening (6:30 AM) will be 12 cc (3 tubes) since we plan additional assays with this sample (lipid panel, inflammatory markers) and 4 cc will be retained as whole blood for future potential analysis. In patients that have signed the optional consent for isolation of genetic material, we will collect an additional 16 cc (4 tubes) at 6:30 AM since this volume is required for isolation of peripheral mononuclear cells. In total, the blood collected will be approximately 174 cc. For patients that consent to isolation of genetic material, the total will be 190 cc. This quantity is much less than during a blood donation. Samples will be frozen at -80°C for research pertaining to metabolic effects of OSA, with the consent of participants. A morning urine sample will be collected for measurement of catecholamines.

Morning procedures:

The PSG montage will be disconnected. One IV is removed, leaving the other IV in place for use during later glucose tolerance test. Then peripheral artery tonometry, DEXA scanning, and OGTT will be performed as follows:

Peripheral arterial tonometry (EndoPAT). The subject will be in the supine position. A blood pressure cuff is placed on the non-dominant arm while the contralateral arm is used for control comparisons. Baseline measurements will be taken for 5 minutes, during 5-min occlusion of the brachial artery by inflation of the automated cuff 50 mmHg above systolic blood pressure, and for 5 minutes upon release of the cuff. Endothelium-mediated vasodilation is assessed using a finger pulse wave amplifier. The reactive hyperemia index (RHI) and the augmentation index (AI) will be derived by software and used as metrics of endothelial function and arterial stiffness respectively.

Oral glucose tolerance test (OGTT). From the indwelling antecubital IV, baseline insulin (gold top tube, 4 cc) and glucose (grey top tube, 4 cc) will be obtained. The patient will be given a 75 g glucose solution to drink within 5

minutes. Blood samples of insulin and glucose are then collected at 30, 60, 90, and 120 minutes after drinking the glucose solution. They will be asked, if possible, to remain awake during the OGTT.

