Dual-energy X-ray absorptiometry (DEXA). After the baseline glucose level for the OGTT has been drawn and the patient has consumed the glucose solution, they will undergo a DEXA scan. The DEXA scan will be used to estimate fat mass, which will be one of the variables analyzed as a predictor of FFA elevation.

Subjects may eat breakfast after the OGTT testing is completed

To minimize the impact of sleep loss on driving safety, subjects are asked to either (1) arrange for an alternate means of transportation home (this is mentioned on the consent or to (2) sleep as needed for up to 4 additional hours before discharge.

Repeat sleep testing:

Repeat sleep tests may be requested from the subject under the following circumstances:

- (1) A technical problem with data acquisition including PSG lead failure/artifacts, incomplete blood collection from IV insertion or maintenance problems.
- (2) Poor sleep efficiency <50% of time in bed

If the initial sleep study meets these criteria and a repeat test is deemed necessary by the PI, then the repeat testing will be scheduled at least 1 week following the initial study.

Scoring. Sleep will be scored according to Rechtschaffen and Kales criteria. Respiratory events will be scored according to AASM criteria. Apneas will be considered present when there is no air flow for >10 seconds. Obstructive apneas will be considered present when apneas are associated with positive strain gauge deflections indicating thoracic movement. Apneas will be considered central in origin when cessation of air flow is not accompanied by thoracic movement as measured by the strain gauge. Mixed apneas will be defined by episodes of no air movement resulting from central apnea followed by obstruction. Hypopneas will be scored for reductions in airflow of 30% lasting >10 seconds accompanied by either an arousal or fall in oxyhemoglobin saturation of 3% or greater.

Data Analysis and Anticipated Outcomes:

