Study-related assessments will not be charged to the subject. Parking fees will be paid. Subjects will be responsible for any treatment of conditions that are uncovered as part of the study evaluations or if they are injured as a result of being in the study.

8. Benefits

a. Description of the probable benefits for the participant and for society.

There are no direct benefits to participants for being in this study. This study will help researchers learn whether OSA causes nocturnal FFA elevations and whether CPAP is effective in preventing the elevations.

9. Payment and Remuneration

a. Detail compensation for participants including possible total compensation, proposed bonus, and any proposed reductions or penalties for not completing the protocol.

Participants will be paid up to \$600 for completing all parts of this study, based on the following procedures:

- \$200 for each sleep study (2 visits)
- \$25 for each oral glucose tolerance test and EndoPAT test (done after each of the 2 visits)
- \$50 for a DEXA scan (only done once)
- \$100 study completion bonus for participants who are able to keep their appointments as originally scheduled. They will forfeit this bonus if they must reschedule their visit(s).
- They will also receive parking reimbursement so there is no fee to come to our laboratory.

10. Costs

a. Detail costs of study procedure(s) or drug (s) or substance(s) to participants and identify who will pay for them.

Participants will not be billed for study procedures. Polysomnograms and blood tests will be billed to the study at standard CRU rates

Reference List

1. Jun, J.C., et al., *Effects of sleep apnea on nocturnal free fatty acids in subjects with heart failure*. *Sleep*, 2011. **34**(9): p. 1207-1213.
2. Schaffer, J.E., *Lipotoxicity: when tissues overeat*. *Curr.Opin.Lipidol.*, 2003. **14**(3): p. 281-287.
3. Young, T., et al., *The occurrence of sleep-disordered breathing among middle-aged adults*. *N Engl J Med*, 1993. **328**(17): p. 1230-1235.
4. Jun, J. and V.Y. Polotsky, *Metabolic consequences of sleep-disordered breathing*. *ILAR J*, 2009. **50**(3): p. 289-306.
5. Punjabi, N.M., et al., *Sleep-disordered breathing and mortality: a prospective cohort study*. *PLoS Med*, 2009. **6**(8): p. e1000132.
6. Amaro, A.C., et al., *The use of nasal dilator strips as a placebo for trials evaluating continuous positive airway pressure*. *Clinics (Sao Paulo)*, 2012. **67**(5): p. 469-74.

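### The DEXA scan falls inside the OGTT at only one of the two visits, so each participant's paired glucose tolerance tests are run under different procedures (low severity; the primary FFA outcome is not affected)

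*Combined protocol and SAP*

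**What the plan says.** The relevant statements are in different sections of the combined protocol and SAP.

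- **Timing of the scan (Section 4a, Morning procedures, DEXA paragraph):** the baseline draw comes first; then, once "the patient has consumed the glucose solution, they will undergo a DEXA scan". Its stated purpose is to estimate fat mass as a predictor of FFA elevation.
- **OGTT sampling (Section 4a, OGTT paragraph):** "Blood samples of insulin and glucose are then collected at 30, 60, 90, and 120 minutes after drinking the glucose solution". The only instruction on behaviour during the test is to stay awake if possible.
- **Number of visits (Section 4b):** "Each study subject will make two overnight visits to the sleep lab". Section 4a puts the two nights in random order.
- **Number of scans and tests (Section 9):** the dollar amounts listed include "25 for each oral glucose tolerance test and EndoPAT test (done after each of the 2 visits" and "50 for a DEXA scan (only done once".
- **Introductory list (Section 4a, Morning procedures):** "Then peripheral artery tonometry, DEXA scanning, and OGTT will be performed as follows". This names the scan before the OGTT, but the detailed text below it puts the scan after the drink.

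Section 2 includes impaired glucose tolerance after CPAP withdrawal among the Aim 1 hypotheses. Study Statistics uses the morning OGTT again as a possible downstream effect of FFA elevation.

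**The concern.** Read alone, the DEXA paragraph suggests that every OGTT includes a scan, in which case the two mornings would match. Only Section 9 shows that the scan is done once. The two OGTTs that each participant contributes to the CPAP-versus-NDS comparison therefore differ in procedure as well as in condition.

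Nothing in the documents ties the scan to a visit number or a condition, or describes a matching routine on the other morning. The mixed model described for FFA has condition as its fixed factor. Variables measured once are to be compared by one-way ANOVA, and the downstream regressions name age, sex and BMI as examples of confounders. No visit or period term appears in any of these, so the stated analyses would not remove an effect of the scan if there were one.

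At stake is the precision of the glucose tolerance contrast and, under uneven scheduling, its freedom from bias.

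**Working it through.** **Step 1. How many scans and OGTTs?** Section 9 gives $200 per sleep study (2 visits), $25 for OGTT and EndoPAT at each visit, $50 for DEXA, a $100 bonus, and a stated maximum of $600.

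- One scan, with OGTT and EndoPAT paid as one item per visit: 2 × 200 + 2 × 25 + 1 × 50 + 100 = 600. This reproduces the stated total.
- Two scans, same pairing: 400 + 50 + 100 + 100 = 650.
- One scan, with $25 for each test separately: 400 + 100 + 50 + 100 = 650. Two scans on that basis: 700.

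Only one scan and two OGTT/EndoPAT sessions give $600, so the payment list is consistent with itself.

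**Step 2. Is the scan inside the test?** Take the drink as time 0, with samples at 30, 60, 90 and 120 minutes. The DEXA paragraph ties the scan to the baseline draw and the drink, and says nothing about waiting for the last sample. On the natural reading the scan falls between 0 and 120 minutes.

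**Step 3. Effect on the contrast.** Let d be a constant shift in an OGTT value caused by a scan during the test (an assumption; the documents give no value). Let p be the share of participants scanned on the NDS morning. The NDS-minus-CPAP difference gains +d for those participants and −d for the rest. Hence:

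- Bias in the mean = pd − (1 − p)d = d(2p − 1).
- Added variance of the paired difference = d² − d²(2p − 1)² = 4p(1 − p)d².

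| p (scan on NDS morning) | Bias | Added variance |
|---|---|---|
| 0 | −d | 0 |
| 0.25 | −0.5d | 0.75d² |
| 0.4 | −0.2d | 0.96d² |
| 0.5 | 0 | d² |
| 0.6 | +0.2d | 0.96d² |
| 0.75 | +0.5d | 0.75d² |
| 1 | +d | 0 |

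**Step 4. Scan fixed to one visit number.** Assume simple randomisation of order; the documents do not say whether order is balanced. Then p is 0.5 in expectation and varies only by chance. The 95% binomial range is:

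- N = 78 (the required sample size): p from 0.385 to 0.615, so bias within about ±0.23d.
- N = 92 (target enrolment): p from 0.402 to 0.598, so bias within about ±0.20d.

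**Step 5. Illustrative scale.** The documents give no SD for a paired glucose difference. Assume 25 mg/dL and p = 0.5. SD inflation = √(25² + d²)/25 − 1.

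| Assumed d (mg/dL) | SD inflation |
|---|---|
| 1 | 0.1% |
| 2 | 0.3% |
| 5 | 2.0% |
| 10 | 7.7% |
| 15 | 16.6% |

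Both d and the SD are assumptions. The range includes values at which nothing of practical importance happens.

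**The case against.** The strongest reply is that no harm has been shown. The documents give no effect of a scan on glucose or insulin. Samples are 30 minutes apart, and nothing indicates that a scan cannot fit between two of them. Order is randomised, so if the scan is always done at the same visit number its effect is a period effect, balanced across conditions in expectation. The primary outcome and the sample size, which rests on a sex difference in FFA change, are untouched. All of this stands, and it sets the low severity.

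A reader might infer more, and the documents do not support these inferences:

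- **That the CPAP-versus-NDS comparison is biased.** Bias requires scans to fall unevenly by condition, and nothing in the documents says that they will.
- **That variance rises in every case.** The added term is zero when all scans fall on one condition, although the bias is then the full d.
- **That the participant rests on the morning without a scan, or that draws are delayed on the other.** Activity on the morning without a scan is not described, and no displaced draw is mentioned.
- **That Section 4a contradicts itself on the order.** The introductory list defers to the text that follows it, and that text gives the timing explicitly. This is a matter for tidying.

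The reply does not remove the asymmetry itself. One OGTT in each pair includes a scan, the visit is unspecified, and the analyses as stated do not account for it.

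**Conclusion.** The point holds as a cheap improvement of low severity. From the text, each participant who completes both visits has one OGTT with a scan inside it and one without.

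If the scan is fixed to one visit number under randomised order, the consequence is mainly noise, at most d² added to the variance of the paired difference, with chance bias of about ±0.2d at the planned numbers. If scheduling lets the scan drift towards one condition, the bias is d(2p − 1), for example 0.2d at a 60:40 split.

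These results assume a constant additive d that is the same under both conditions. Its size is unknown and may be negligible, so materiality is not demonstrated. The point is confined to glucose tolerance. The primary nocturnal FFA outcome is sampled until the morning awakening draw, before these procedures begin, and no sample-size or power figure changes.

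**What to change.** Amend the DEXA paragraph of Section 4a so that the scan is done after the 120-minute OGTT sample. Add that the OGTT routine is the same on both mornings, and reorder the introductory list under Morning procedures to match. Both the bias term and the variance term from scanning during the test then become zero, whichever visit carries the scan.

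Scanning before the baseline draw is less good. On that one morning the OGTT would start later and follow the movement and positioning for the scan, so the two tests would still differ.

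The cost is a short text amendment and one visit that lasts longer by the length of a scan. No procedure or staff is added, and the scan's purpose of estimating fat mass does not depend on its being done during the OGTT.
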